3.2.22 History of prior therapy with belinostat or MLN4924 (pevonedistat).

3.2.23 Active gastrointestinal (GI) conditions that might predispose to drug intolerance or poor drug absorption.

3.2.24 Known hepatic cirrhosis.

3.2.25 Known moderate to severe chronic obstructive pulmonary disease, interstitial lung disease, and pulmonary fibrosis.

3.2.26 No other prior malignancy is allowed except for the following:

- *In situ* cervical cancer,
- Adequately treated basal cell or squamous cell skin cancer,
- Adequately treated Stage I or II cancer from which the patient is currently in complete remission, and
- Any other cancer from which the patient has been disease-free for at least 1 year.

3.2.27 Medical, psychological, or social condition that, in the opinion of the investigator, may increase the patient's risk, interfere with the patient's participation in the study, or hinder evaluation of study results.

3.2.28 Pregnant or nursing. Women of childbearing potential must have a negative serum pregnancy test performed within 7 days prior to the start of study therapy.

Note: Pregnant women are excluded from this study because MLN4924 (pevonedistat) is a NEDD8 inhibitor with the potential for teratogenic or abortifacient effects and because belinostat may cause teratogenicity and/or embryo-fetal lethality by virtue of targeting actively dividing cells. Because there is an unknown but potential risk for AEs in nursing infants secondary to treatment of the mother with MLN4924 (pevonedistat) or belinostat, breastfeeding should be discontinued if the mother is treated with MLN4924 (pevonedistat)/belinostat.

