5. BIOMARKER, CORRELATIVE, AND SPECIAL STUDIES

5.1 [REDACTED]

[REDACTED]	[REDACTED]	[REDACTED]	[REDACTED]	[REDACTED]	[REDACTED]	[REDACTED]	[REDACTED]	[REDACTED]
[REDACTED]	[REDACTED]	[REDACTED]	[REDACTED]	[REDACTED]	[REDACTED]	[REDACTED]	[REDACTED]	[REDACTED]
[REDACTED]	[REDACTED]	[REDACTED]	[REDACTED]	[REDACTED]	[REDACTED]	[REDACTED]	[REDACTED]	[REDACTED]
[REDACTED]	[REDACTED]	[REDACTED]	[REDACTED]	[REDACTED]	[REDACTED]	[REDACTED]	[REDACTED]	[REDACTED]
[REDACTED]	[REDACTED]	[REDACTED]	[REDACTED]	[REDACTED]	[REDACTED]	[REDACTED]	[REDACTED]	[REDACTED]
[REDACTED]	[REDACTED]	[REDACTED]	[REDACTED]	[REDACTED]	[REDACTED]	[REDACTED]	[REDACTED]	[REDACTED] L
[REDACTED]	[REDACTED]	[REDACTED]	[REDACTED]	[REDACTED]	[REDACTED] ent	[REDACTED]	[REDACTED]	[REDACTED]

Priority	Biomarker Name	Biomarker Assay	Biomarker Type and Purpose	M/O	Timing	Specimen	Quantity Needed	Laboratory
6	[REDACTED]	[REDACTED]	[REDACTED]	[REDACTED]	[REDACTED]	[REDACTED]	[REDACTED]	[REDACTED]
7	Belinostat PK profile	PK profile	Integrated PK profiling	M	Cycle 1 Day 1-2: Belinostat sampling schedule ^a	Blood	5 mL	APC, [name], Johns Hopkins University
8	MLN4924 (pevonedistat) PK profile	PK profile	Integrated PK profiling	M	Cycle 1 Day 1-2: MLN4924 (pevonedistat) sampling schedule ^b	Blood	5 mL	QPS, LLC

^a See belinostat sampling schedule, Section 5.3.3.2.1.

^b See MLN4924 (pevonedistat) sampling Section 5.3.3.1.1.

^c Blood collection is mandatory provided that there are anticipated to be at least 10% blasts in the baseline sample (a determination made based on review of routine clinical CBC and differential). When blood is not anticipated to meet the 10% blast sampling threshold, and if an optional bone marrow is being done, collection of aspirate is allowed in lieu of blood sampling if the aspirate sample is anticipated to meet the 10% blast sampling threshold.

^d Blood collection is mandatory provided that there are anticipated to be at least 40% blasts in the baseline sample (a determination made based on review of routine clinical CBC and differential). When blood is not anticipated to meet the 40% blast sampling threshold, and if an optional bone marrow is being done, collection of aspirate is allowed in lieu of blood sampling if the aspirate sample is anticipated to meet the 40% blast sampling threshold.

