5.3.3.2 Belinostat PK Studies

[REDACTED]

[REDACTED]

- Whenever possible collect PK specimens from a venous access point that has not been used for drug infusion.
- Collect 4-6 mL of venous blood into tubes containing sodium heparin (see tube ordering information below) at the time points specified below for belinostat PK analysis.
- GENTLY invert the tube 8-10 times after collection to avoid sample hemolysis.
- For belinostat, sample collection will occur at these approximate time points on Cycle 1, starting on Day 1, timed from the END of the belinostat infusion:
 - pre-belinostat infusion
 - 5 minutes (± 1 min) prior to the END of belinostat infusion
 - 15 minutes (± 10 min) after the END of the belinostat infusion and then
 - 30 minutes (± 10 min)
 - 1 hr (± 10 min)
 - 2 hrs (± 10 min)
 - 4 hrs (± 10 min)
 - 6 hrs (± 30 min)
 - 8 hrs (± 45 min)
 - and 24 hrs (± 4 hrs) after the END of the belinostat infusion.

Note: if samples cannot be obtained within the stated time point window, it's preferable to draw a sample as close to the time point as possible rather than omitting the sample – be sure the actual time of collection is recorded.

5.3.3.2.1.1 Belinostat PK supply ordering

Each participating site will procure sodium heparin tubes. Recommended items/vendors include:

- BD (Becton Dickinson) Catalog No. 23-021-017 (Manufacturer No. BD 367878): sodium heparin-containing plastic green-top tubes 6 mL
- Fisher Scientific Catalog No. 367878: sodium heparin-containing plastic green-top tubes 6 mL

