6. TREATMENT PLAN

6.1 Agent Administration

This will be a two-part phase 1 dose-escalation and exploratory dose-expansion study of MLN4924 (pevonedistat) in combination with belinostat. Part A will consist of a 3+3 dose-escalation phase of the combination to assess its safety and tolerability and identify an MTD/tentative RP2D. After the MTD has been established, Part B of the study will involve an exploratory-dose expansion study of 12 additional patients who will be enrolled at the tentative RP2D to gain further insights into the safety of the regimen. MLN4929 (pevonedistat) and belinostat dose rounding is allowed per institutional guidelines.

Treatment will be administered on an outpatient basis. Cycles are to be repeated every 21 days. Reported adverse events and potential risks are described in Section 10. Appropriate dose modifications are described in Section 7. Other than hydroxyurea during the first 5 days of study treatment, no investigational or commercial agents or therapies other than those described below may be administered with the intent to treat the patient's malignancy.

Dose Escalation Schedule				
Dose Level	Belinostat		MLN4924 (pevonedistat)	
	Dose (mg/m²/day)	Administration and Schedule	Dose (mg/m²/day)	Administration and Schedule
-1	800	Intravenously over 30 minutes once daily on Days 1-5 of each 21-day cycle	15	Intravenously over 60 minutes once daily on Days 1, 3, & 5 of each 21-day cycle**
1*	800		20	
2	800		25	
3	800		37	
4	1000		37	
5	1000		50	
6***	1000		59	

* Starting dose level

** When both drugs are given on the same day (Days 1, 3, 5), start the MLN4924 (pevonedistat) infusion within 60 mins after the completion of belinostat infusion.

*** The 59 mg/m² level will not begin until the NCI/CTEP, Principal Investigator and Takeda have closely examined the toxicity, PK and clinical data from the 50 mg/m² cohort. Takeda must give written approval for the 59 mg/m² to begin.

Regimen Description				
Agent	Premedication; Precautions	Dose And Route	Schedule	Cycle Length
Belinostat	See Section 6.4	In 250 mL 0.9% NaCl IV over 30 (± 5 min)*** Dose per assigned dose level.	Days 1-5 (week 1)	21 days (3 weeks)
MLN4924 (pevonedistat)	See Section 6.4	In 250 mL D5W or 0.9% NS IV over 60 min (± 10 min)* Infusion to start within 60 minutes after belinostat infusion ends. Dose per assigned dose level.	Days 1, 3, & 5 (week 1)**	

IV = Intravenously; D5W = dextrose 5% in water; NS = normal saline.

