6.1.1 MLN4924 (pevonedistat)

MLN4924 (pevonedistat) will be given intravenously over 60 minutes (± 10 minutes) through central or peripheral venous access. The IV infusion can be slowed or stopped and restarted for any associated infusion-related reactions. The total time from the IV preparation to end of IV infusion must not exceed 6 hours if stored at room temperature. Alternatively, the prepared IV bag may be stored for up to 18 hours at 2°C to 8°C (36-46°F). After 18 hours of storage at 2°C to 8°C (36-46°F), the prepared IV bag must be used within 3 hours upon coming to room temperature or must be discarded. When both drugs are given on the same day (Days 1, 3, 5), start the MLN4924 (pevonedistat) infusion within 60 min after the completion of belinostat infusion.

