9.4.2 Statistical Analyses for Secondary Objectives

Toxicities: AEs and SAEs, dosing levels, treatment received, best clinical response, and demographics will be listed. Basic descriptive statistics will be used to summarize toxicities related to the study drugs by grade, and all toxicities, whether related or unrelated to the study drugs.

Anti-tumor activity: For the response rate calculations, all study reports will contain at least a section with all enrolled patients. Other sections of the reports may detail the response rate for response-evaluable patients only. All response rate analyses based on a subset of patients will be accompanied by explanations of which patients were excluded and the reasons; 95% confidence limits will be given. For patients who do not have disease progression or have not died at time of analysis, the last date the patient was known to be alive and progression free will be used for duration of response analysis. If there are at least 3 responses, duration of response and time to response will be summarized by the first, second, and third quantiles and illustrated by a Kaplan-Meier plot.

PK interactions: PK parameters in MLN4924 (pevonedistat) and in belinostat will be calculated using standard non-compartmental methods and summarized as geometric mean and geometric coefficient of variation. C_{max} and the times needed to reach these concentrations (t_{max}) will be assessed by inspection of the concentration versus time plots. The AUC will be calculated from time zero to infinity ($AUC_{0-\infty}$). V_d and $t_{1/2}$ will also be calculated accordingly. To discover any potential PK interactions between the 2 agents, each PK parameter will be compared with each referenced PK parameter for those who receive single-agent at the same amount dose by a one-sample t-test. The normality of the PK parameters will be checked, and data transformation may be performed if data are highly skewed.

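### Day 1 belinostat Cmax and tmax cannot show an effect of pevonedistat, and Day 1 AUC understates one, yet section 9.4.2 compares every PK parameter with single-agent values by a one-sample t-test

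*Combined protocol and SAP*

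**What the plan says.** Objective 1.2.4 is to describe PK interactions between the two drugs. For this, section 9.4.2 states that "each PK parameter will be compared with each referenced PK parameter for those who receive single-agent at the same amount dose by a one-sample t-test". Parameters named there are Cmax, tmax, AUC from zero to infinity, Vd and half-life. No reference value, source, sample size, SD or significance level is given.

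The design facts that bear on the belinostat side are:

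- **Occasion.** The assay table in section 5.1 lists "Cycle 1 Day 1-2: Belinostat sampling schedule" and no later belinostat profile.
- **Prior exposure.** Section 3.2.22 excludes patients previously treated with either drug.
- **Order on Day 1.** Belinostat is given "Intravenously over 30 minutes once daily on Days 1-5 of each 21-day cycle" (section 6.1). Section 6.1.1 then says to "start the MLN4924 (pevonedistat) infusion within 60 min after the completion of belinostat infusion".
- **Sampling.** Section 5.3.3.2 takes the near-peak sample 5 minutes "prior to the END of belinostat infusion". Later samples follow at 15 and 30 minutes and at 1, 2, 4, 6, 8 and 24 hours after the end of infusion, the last with a window of ±4 hours. It adds: "be sure the actual time of collection is recorded".

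Section 9.4 calls all analyses descriptive, and section 2.5 describes the interaction aim as preliminary.

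**The concern.** The comparison runs over every parameter of both drugs, but the order of dosing makes the belinostat parameters unequal as evidence. A constant-rate infusion peaks at its end, and at that moment the patient has received no pevonedistat. A difference in Day 1 belinostat Cmax or tmax from the single-agent reference would reflect population, assay or chance. Agreement would say nothing about the combination either. AUC mixes a stretch before pevonedistat with one after it, so a real effect on belinostat clearance is pulled toward a ratio of 1.

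Two smaller matters sit alongside. Belinostat is infused again on Day 2, and the visible sampling text does not say that the 24-hour sample must come before that dose. And a one-sample t-test has no term for the sampling error of the reference mean.

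At stake is a report on objective 1.2.4 that states an interaction, or the absence of one, on parameters that could not have shown it.

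**Working it through.** The plan states no power, level or expected effect for this comparison, so there is no figure of its own to reproduce.

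**1. Share of belinostat AUC after pevonedistat starts.** Inputs: infusion time T = 0.5 h (section 6.1), half-life 0.3 to 1.3 h (section 2.2.1.2), gap d = 0 to 1 h (section 6.1.1). Assumption: one compartment, k = ln 2 / half-life. Then

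f = [(1 − e^(−kT)) / (kT)] × e^(−kd).

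For half-life 0.3 h and d = 1 h: k = 2.31, kT = 1.155, first factor 0.593, e^(−2.31) = 0.099, so f = 0.059. If clearance is halved from the start of pevonedistat (assumption), the later part of the AUC doubles and the ratio is 1 + f.

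| Half-life | Gap | Share before (1 − f) | Share after (f) | Ratio shown (full effect 2.0) |
|---|---|---|---|---|
| 0.3 h | 0 | 0.407 | 0.593 | 1.59 |
| 0.3 h | 30 min | 0.813 | 0.187 | 1.19 |
| 0.3 h | 60 min | 0.941 | 0.059 | 1.06 |
| 1.3 h | 0 | 0.122 | 0.878 | 1.88 |
| 1.3 h | 30 min | 0.328 | 0.672 | 1.67 |
| 1.3 h | 60 min | 0.485 | 0.515 | 1.52 |

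**2. Sampled Cmax.** With no gap, the 15-minute sample can exceed the sample taken before the end of infusion and could then be touched by pevonedistat. In the same model with clearance halved, and draws at 5, 15 or 25 minutes (the 15-minute point ±10), sampled Cmax rises by at most about 7%. If pevonedistat starts after that draw, it does not move.

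**3. Half-life as a substitute.** In the one-compartment model, half-life fitted to the 2 to 8 h samples would show the full 2.0. I checked this in a two-compartment illustration: central elimination, 10% of AUC in a phase with a 5 h half-life, clearance halved at pevonedistat start.

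| Fast phase | Fitted half-life ratio, 2–8 h | Day 1 AUC ratio |
|---|---|---|
| 0.3 h | 0.74 to 0.96 | 1.14 to 1.63 |
| 1.3 h | about 1.85 | 1.55 to 1.89 |

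With the short fast phase, half-life moves the wrong way. AUC is diluted but keeps its direction.

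**4. The 24-hour sample.** If Day 2 dosing is at the same clock time (assumption), the Day 2 infusion runs from 23.5 to 24 h after the Day 1 end of infusion, and the permitted window is 20 to 28 h. In the one-compartment model, Day 1 drug left at 24 h is at most 3 × 10⁻⁶ of the end-of-infusion level. A sample at the end of the Day 2 infusion, if used as Day 1 data, would inflate the linear trapezoidal AUC to the last sample 4.8-fold (1.3 h) to 11.9-fold (0.3 h).

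**5. One-sample t-test.** With n trial patients, m reference patients, equal SDs and a two-sided 5% level (all assumed), the true error is 2 × P(t[n−1] > t_crit / √(1 + n/m)). For n = 18, m = 20: t_crit = 2.110, √1.9 = 1.378, threshold 1.531, error 0.144.

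| n | m = 6 | m = 20 | m = 100 |
|---|---|---|---|
| 3 | 7.2% | 5.7% | 5.1% |
| 6 | 12.9% | 7.4% | 5.5% |
| 12 | 23.0% | 11.0% | 6.2% |
| 18 | 30.6% | 14.4% | 6.9% |

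Here 3 and 6 are escalation cohort sizes (section 6.3), 12 is the expansion cohort (section 6.4), and 18 is 6 + 12.

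**The case against.** The best reply is that this is a preliminary, descriptive objective with no decision rule, so a loosely worded comparison does little harm. That stands as a limit on the consequence. It does not make Cmax and tmax informative, and section 9.4.2 still names a test whose purpose is to find interactions.

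A second reply concerns the 24-hour sample. Text just before the sampling list in section 5.3.3.2 is redacted, actual draw times are recorded, and a competent non-compartmental analysis would not normally assign a post-dose Day 2 sample to Day 1. This largely stands. A reader might infer that the Day 1 profiles will be contaminated; the documents support only that they could be, and that no visible rule prevents it.

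Third, the error rates in step 5 need a level, SDs and a reference size that the documents do not give. The relevant n is also open. The belinostat dose is 800 mg/m² at levels −1 to 3 and 1000 mg/m² at levels 4 to 6, so a same-dose comparison could pool levels. Both points stand: the table shows direction and range, not the trial's actual error rate.

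Finally, a reader might conclude that terminal half-life rescues the Day 1 belinostat comparison. Step 3 shows that this depends on one-compartment kinetics, which the documents do not establish. It also needs late samples: at a 0.3 h half-life only about 1% of the end-of-infusion concentration remains at 2 h, and assay sensitivity is not stated.

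**Conclusion.** The point holds for the belinostat side of the comparison. True Day 1 Cmax and tmax say nothing about pevonedistat, and sampled Cmax next to nothing. This follows from the dosing order and needs no kinetic model. Day 1 AUC is biased toward no interaction for every permitted gap. The size runs from mild (1.88 in place of 2.0) to nearly complete (1.06), and rests on the one-compartment form and an immediate halving of clearance. The t-test understates uncertainty by an amount that cannot be fixed from the documents.

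It would go too far to infer that the interaction objective fails as a whole. Post-dose pevonedistat samples all follow the belinostat infusion, so the comparison of pevonedistat PK with its reference is not affected by the order. Belinostat AUC keeps some information and its direction. Nor does any of this reach the primary objective: the RP2D rule in section 6 does not use these comparisons.

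**What to change.** (a) In section 9.4.2, remove Day 1 belinostat Cmax and tmax from the interaction comparison and report them as essentially single-agent values. State that Day 1 belinostat AUC reflects partial co-exposure, so a ratio near 1 does not rule out an effect of pevonedistat on belinostat. Do not name terminal half-life as the preferred measure.

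(b) In section 5.3.3.2, unless the redacted text already does so, require the 24-hour belinostat PK sample before the Day 2 belinostat infusion. Exclude from Day 1 parameters any sample drawn after that infusion starts; the recorded times identify these.

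(c) Replace the one-sample t-test by geometric mean ratios, in line with the geometric summaries already planned. Give confidence intervals that include the reference study's standard error where its SD and n are available. Otherwise report the ratios descriptively without a test, consistent with section 9.4. State how dose levels sharing a belinostat dose are pooled.

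Cost: one line in section 5.3.3.2, a few sentences in section 9.4.2 and minor analysis work, with no extra samples or visits and no change to dosing. The price is wider intervals and a narrower conclusion on belinostat. Day 1 AUC stays diluted.

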2.2.1.2 Clinical Experience with Belinostat

Belinostat (PXD101, Beleodaq, Spectrum Pharmaceuticals, Inc.), FDA-approved in 2014 for relapsed/refractory peripheral T-cell lymphoma (PTCL), is a hydroxamate derivative that inhibits both class I and II HDACs (pan-HDACi) (Molife *et al.*, 2011). In preclinical studies, it suppresses the growth of and induces apoptosis in a variety of tumor types, both *in vitro* and *in vivo* (Plumb *et al.*, 2003; Qian *et al.*, 2006; Qian *et al.*, 2008; Buckley *et al.*, 2007; Ma *et al.*, 2010). Although the drug has mostly been administered intravenously (IV) in clinical trials, an oral formulation has also been tested (Steele *et al.*, 2011). IV belinostat displays linear PKs with respect to the maximum concentration (C_{max}) and the area under the “concentration time” curve (AUC) (Steele *et al.*, 2008), without significant accumulation (Yeo *et al.*, 2012). The intermediate elimination half-life is 0.3 to 1.3 hrs and independent of dose (Steele *et al.*, 2008). Belinostat PKs are unaltered by concurrent administration with carboplatin and paclitaxel (Lassen *et al.*, 2010). Glucuronidation by UGT1A1 is by far the major route of belinostat elimination in humans (Wang *et al.*, 2013). The drug has 5 major metabolites, which are not expected to have anticancer effects, and the parent drug and metabolites can be quantified in human plasma by means of a validated liquid chromatography-tandem mass spectrometry assay (Kiesel *et al.*, 2013). *In vitro* studies indicate that belinostat is a weak/moderate inhibitor of cytochrome P450 family 2 subfamily C member 8 (CYP2C8) and a moderate to strong inhibitor of CYP2C9.

In a phase 1 study in patients with advanced solid tumors, the MTD of belinostat was 1000 mg/m²

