* May extend or interrupt MLN4924 (pevonedistat) infusion as needed for infusion-related reactions, provided total time from drug reconstitution to end of infusion does not exceed 6 hrs (or within 3 hours of coming to room temperature if previously stored for up to 18 hours as shown in Section 6.1.1).

**Doses of MLN4924 (pevonedistat) must be separated by at least 1 full calendar day. When both drugs are given on the same day (Days 1, 3, 5), start the MLN4924 (pevonedistat) infusion within 60 min after the completion of belinostat infusion.

***May extend belinostat infusion to 3 hrs if infusion-related reactions occur.

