6.1.2 Belinostat

Belinostat will be administered IV over 30 minutes (± 5 minutes) by central or peripheral access through an in-line 0.22-micron filter.

Belinostat infusions may be prolonged up to 3 hrs, if deemed necessary, to ameliorate acute infusion-related reactions (nausea, flushing, rhinitis, vomiting, *etc.*) that may occur during, or immediately following infusion. Once diluted in 250 mL of 0.9% sodium chloride, belinostat may be stored at controlled room temperature (20-25°C) for up to 36 hrs, including the infusion time.

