																		

- A. MLN4924 (pevonedistat): Dose as assigned; IV over 60 minutes (\pm 10 minutes) once daily (QD) on Days 1, 3, and 5 of each 21-day cycle. When both drugs are given on the same day (Days 1, 3, 5), start the MLN4924 (pevonedistat) infusion within 60 mins after the completion of belinostat infusion.
- B. Belinostat: Dose as assigned; IV over 30 minutes QD on Days 1-5 of each 21-day cycle. Infusion may be extended to 3 hours pending patient tolerance.
- Prior to treatment
 - Unless stated otherwise, baseline evaluations are to be conducted within 1 week prior to start of study therapy. Repeat if not within 1 week prior to Cycle 1, Day 1. In the event that the patient's condition is deteriorating, laboratory evaluations should be repeated within 48 hrs prior to initiation of the next cycle of therapy.
 - End of treatment visit occurs after completion of all study treatment.
 - See Section 6.8.
 - Only for patients with a CR, CRi, CRc, CRm, ML-FS, PR, or SD, capture reported clinical status approximately every 2 months for 2 years following end of safety follow-up until disease progression or death. See Section 6.8.
 - Urinalysis to include turbidity and color, pH, specific gravity, protein, ketones, bilirubin, occult blood, nitrite, glucose, and leukocyte esterase. Microscopic analysis should be done at the discretion of the treating physician.
 - Include over-the-counter medications.
 - Sodium, potassium, carbon dioxide content, chloride, creatinine, blood urea nitrogen (BUN), glucose and calcium.
 - Alkaline phosphatase, ALT, AST and total bilirubin assessments must be performed and read prior to each dose of MLN4924 (pevonedistat).
 - Total bilirubin, direct bilirubin, ALP (alkaline phosphatase), AST, ALT, total protein, albumin.
 - Hepatitis serologies and, if needed, HBV viral load testing are to be done \leq 4 weeks prior to the start of therapy. HBV viral load only necessary if patients are Hepatitis B Ab positive.
 - Pre- & post-treatment on Cycle 1 Day 4 and whenever clinically indicated. Patients with risk factors for QT prolongation including CHF, bradyarrhythmias, electrolyte abnormalities or those on other drugs known to prolong the QT/QTc interval, such as Class Ia and III anti-arrhythmics, should be closely monitored as clinically indicated with ECGs and serum electrolytes (magnesium, potassium) while on study treatment. See Section 6.5.

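### Section 9.4.2 matches the single-agent PK reference on dose only, so a prolonged Day 1 belinostat infusion biases Cmax and tmax even with no drug interaction

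*Combined protocol and SAP*

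**What the plan says.** **Infusion time.** Section 6.1.2 gives the nominal rule, "Belinostat will be administered IV over 30 minutes (± 5 minutes) by central or peripheral access", and then the allowance: "Belinostat infusions may be prolonged up to 3 hrs, if deemed necessary, to ameliorate acute infusion-related reactions". A footnote to the regimen table in Section 6.1 repeats it ("May extend belinostat infusion to 3 hrs if infusion-related reactions occur"), as does the Section 11 calendar ("Infusion may be extended to 3 hours pending patient tolerance"). None of the three excepts Cycle 1 Day 1, the dose around which belinostat PK is sampled (Sections 5.1 and 5.3.3.2).

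**Sampling.** In Section 5.3.3.2, times count from the end of the infusion. After the pre-dose sample the next is "5 minutes (± 1 min) prior to the END of belinostat infusion", followed by samples from 15 minutes to 24 hours after the end.

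**Analysis.** Section 9.4.2 specifies non-compartmental methods, with Cmax and tmax taken by inspecting the concentration-time plots. It then states that "each PK parameter will be compared with each referenced PK parameter for those who receive single-agent at the same amount dose", using a one-sample t-test. It names no reference source or values and has no rule for prolonged infusions. Section 5.3.3.2.4 leaves compartmental analysis open as an alternative.

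**Background.** Section 2.2.1.2 describes belinostat PK as linear for Cmax and AUC and adds: "The intermediate elimination half-life is 0.3 to 1.3 hrs and independent of dose". The solid-tumour single-agent phase 1 study described there infused over 30 minutes.

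**The concern.** With a half-life this short, the peak depends heavily on the infusion rate. Giving the same dose more slowly lowers Cmax and delays tmax mechanically. If the reference is matched on dose amount alone, that shift enters the comparison as though pevonedistat had caused it. It runs in the direction that would offset a genuine increase in belinostat exposure.

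Describing PK interactions is a stated secondary objective (1.2.4). PK data from the 50 mg/m² pevonedistat cohort are also among the data to be examined before the 59 mg/m² level may begin (Section 6.1). Prolongation is given because of reactions, so the affected patients are not a random subset.

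**Working it through.** The documents state no expected Cmax change, so there is no planned figure to reproduce. The size follows from their infusion times and half-life range, plus one assumption: a one-compartment model with constant-rate infusion.

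**Inputs.** T = 0.5 h nominal and up to 3 h (Section 6.1.2); half-life 0.3 to 1.3 h (Section 2.2.1.2); sampling times (Section 5.3.3.2).

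**One patient's Cmax.** With k = ln 2 / half-life, Cmax(T) = (Dose/T)/(kV) × (1 − exp(−kT)). The 3 h to 0.5 h ratio is (0.5/3) × (1 − exp(−3k)) / (1 − exp(−0.5k)).

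- Half-life 0.3 h: 0.1667 × 0.9990 / 0.6850 = 0.243.
- Half-life 1.3 h: 0.1667 × 0.7980 / 0.2340 = 0.568.

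| Half-life (h) | k (per h) | Ratio, 3 h to 0.5 h | True Cmax lower by | Highest sampled value lower by | True Cmax lower by, 1 h infusion |
|---|---|---|---|---|---|
| 0.3 | 2.310 | 0.243 | 75.7% | 73.1% | 34.3% |
| 0.8 | 0.866 | 0.439 | 56.1% | 49.4% | 17.6% |
| 1.3 | 0.533 | 0.568 | 43.2% | 35.8% | 11.7% |

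The fifth column compares the largest concentration that the protocol's sampling times would catch at each duration. Under the same model tmax, counted from the start of infusion, moves from 0.5 h to 3 h.

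**Group summary.** One such patient among n multiplies the geometric mean Cmax by ratio^(1/n).

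- n = 3: 0.624 to 0.828 (17-38% lower)
- n = 6: 0.790 to 0.910 (9-21% lower)
- n = 12: 0.889 to 0.954 (5-11% lower)
- n = 18: 0.924 to 0.969 (3-8% lower)

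At n = 6, one 3 h infusion would therefore cancel a true rise in geometric mean Cmax of 10% (1/0.910) to 27% (1/0.790).

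**The t-test.** This was simulated on the log scale with no interaction, an assumed between-patient CV of 30% or 50%, an assumed two-sided 5% level, and n = 6 or 12. The Cmax ratio for prolonged patients was 0.568 or 0.243. Rejection rates were 0.8-5.1% with one prolonged patient, 2.7-8.5% with two and 10.4-21.7% with three. A single outlier shifts the mean but widens the variance at least as much.

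**AUC.** Under linear PK the true AUC from zero to infinity does not depend on infusion time. The non-compartmental estimate does, because nothing is sampled between pre-dose and 5 minutes before the end. The trapezoid draws a straight line from zero across what is nearly a plateau. With linear-up/log-down trapezoids on the protocol's schedule, estimated over true AUC is 0.65 to 0.90 for a 3 h infusion and 0.92 to 0.99 for 30 minutes. That is an apparent deficit of 8% (1 − 0.903/0.986) to 29% (1 − 0.651/0.918).

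**Infusion slowed partway.** If half the dose runs in 15 minutes and the rest is slowed to end at 3 h, the true peak is 36-47% below the 30-minute peak and falls where no sample is taken. Estimated AUC drops to 0.36-0.68 of true.

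**The case against.** The strongest reply is that the full 3 h case is extreme. Prior belinostat is an exclusion (3.2.22), so Day 1 is the first exposure. Extension responds to reactions, and one that follows the Day 1 infusion can only lengthen later, unsampled infusions. The 50%, 31% and 31% rates for nausea, vomiting and flushing in Section 2.2.1.2 are study-wide, all-grade figures. The belinostat risk list (10.1.1.2) puts flushing at 20% or less and lists infusion-related reaction among events with insufficient evidence of causation. All of this stands: the frequency is unknown and may be low.

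Belinostat also has only two assigned doses, 800 and 1000 mg/m², so matching on dose permits pooling across levels. Section 6.4 adds 12 patients to at least six at the RP2D, which makes 18; Section 9.1 describes 12 in total. The 12- and 18-patient figures may therefore be nearer the mark than those for three or six. The analysis is descriptive (9.4), and the single-agent reference is unnamed, so its infusion time is not known for certain.

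A reader might infer that one prolonged infusion would probably yield a false interaction finding. The simulation does not support that. A reader might also infer that such patients distort the exposure goals in Section 2.5. They do not: a lower peak after a slow infusion is that patient's real exposure. Dropping them from PK-PD correlations would select on a post-dose reaction and could remove high-exposure patients.

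The gap itself is not answered. Section 9.4.2 has no rule for a departure that the protocol expressly allows on the sampled day. The compartmental option does not close it while 9.4.2 specifies non-compartmental parameters and a plot-read Cmax.

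**Conclusion.** The concern holds as a bias and precision problem in the belinostat Cmax and tmax comparison. A full 3 h Day 1 infusion lowers that patient's true Cmax by 43-76%, or about 36-73% as sampled. One such patient lowers the geometric mean by 9-21% at n = 6 and 5-11% at n = 12. A 1 h infusion lowers the patient's Cmax by about 12-34%.

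These sizes rest on an assumed one-compartment, constant-rate model. How often the problem would arise cannot be judged from the documents. The firmer risk is that a real exposure increase is masked, not that the test falsely rejects. It would be tempting to treat AUC as a safe fallback because true AUC is unaffected, but the planned sampling and non-compartmental estimate do not deliver that for long infusions.

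**What to change.** In Section 9.4.2:

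- Use actual infusion start and stop times for every Day 1 belinostat dose.
- For Cmax and tmax, match the single-agent reference on infusion duration as well as dose. The main interaction comparison then uses Day 1 infusions of 30 (±5) minutes. List prolonged infusions separately and add a sensitivity comparison of all patients.
- For prolonged infusions, estimate AUC, half-life and Vd with the compartmental option in Section 5.3.3.2.4, entering the actual infusion times.
- Keep every patient in the exposure and PK-PD analyses under goals 2 and 3 of Section 2.5.

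The cost is a few sentences of analysis text and the use of infusion times, whose end points the sampling schedule already requires. The main Cmax and tmax comparison loses a few patients. Leaving reactors out of it may introduce selection, which the sensitivity comparison would show. No change to the infusion rule is implied.
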